PROTOCOL TITLE: Evaluating Vitamin C in Septic Shock: A Randomized Double Blind Control
Trial

VERSION DATE: March 17, 2020

ABBREVIATIONS/DEFINITIONS

- BAL: Bronchoalveolar lavage
- BDAC: Biostatistical Design and Analysis Center
- DSMB: Data and Safety Monitoring Board
- ICU: intensive care unit
- LAR: legally authorized representative
- TA: Tracheal aspirate
- Vitamin C: also known as ascorbic acid

PROTOCOL TITLE: Evaluating Vitamin C in Septic Shock: A Randomized Double Blind Control Trial

VERSION DATE: March 17, 2020

STUDY SUMMARY

| | |
|---|---|
| Study Title | Evaluating Vitamin C in Septic Shock: A Randomized Double Blind Control Trial |
| Study Design | Phase 3, randomized double-blind |
| Primary Objective | Evaluate effect of Vitamin C supplementation on survival in patients presenting with septic shock |
| Secondary Objective(s) | Evaluate effect of Vitamin C supplementation on resolution of shock |
| Research Intervention(s)/ Investigational Agents | Vitamin C (ascorbic acid) |
| IND/IDE # (if applicable) | N/A: Exempt |
| Study Population | Patients admitted to ICU with septic shock |
| Sample Size (number of participants) | Approximately 140 Approximately 70 per group (study drug or placebo) |
| Study Duration for Individual Participants | Up to 4 days, plus a Day 28 chart review with no participant interaction |

1.0 Objectives

1.1 Purpose:

This is a randomized, double-blind, placebo-controlled clinical trial to compare Vitamin C versus placebo for patients presenting to the ICU with a diagnosis of septic shock.

Specific Aim 1: Determine if patient survival is improved with the use of Vitamin C.

Hypothesis Aim 1: Compared to placebo, moderate-dose Vitamin C will improve survival.

Specific Aim 2: Determine whether Vitamin C improves secondary clinical outcomes including but not limited to: duration of vasopressor therapy, duration of ICU stay, lactate clearance, and organ failure.

Hypothesis Aim 2: Compared to placebo, moderate-dose Vitamin C will improve clinical outcomes.

Specific Aim 3: Identify individual and clinical characteristics associated with responses to Vitamin C.

Hypothesis Aim 3: Specific characteristics exist that can identify those with a greater chance for a therapeutic response.

2.0 Background

2.1 Significance of Research Question/Purpose:

Sepsis is defined as life threatening organ dysfunction caused by a dysregulated response to infection. Sepsis and septic shock, the latter defined as persistent hypotension refractory to volume resuscitation and requiring vasopressor therapy to maintain adequate blood pressure, are common reasons for admission to the intensive care unit¹. It is estimated that approximately 1 million Americans are diagnosed every year². Despite concerted efforts focused on early recognition and stabilization of septic patients, mortality rates of patients admitted with septic shock remain high at 25%-50%¹ and survival is still associated with significant comorbidity³. This is of particular importance when sepsis-associated organ failure is prolonged, as the extended recovery period keeps patients vulnerable to adverse effects associated with prolonged ICU stays (e.g., myopathy, delirium). All of this highlights the need for novel effective therapies.

The main tenets of therapy in sepsis have been focused on early recognition, hemodynamic stabilization (correction of low blood pressure) and antimicrobial therapies. This involves early aggressive fluid resuscitation and vasopressor therapy (medications such as epinephrine which increase blood pressure), as well as early empiric antibiotic therapy and effective source control, the latter of which consistently correlates with survival^{1,3,4}. Over the last two decades, most efforts to improve outcomes in sepsis have focused on resuscitation at the systemic level (e.g. blood pressure and cardiac output goals). Unfortunately, although several 'targeted' systemic resuscitation studies have shown promise during early studies (e.g. early goal directed therapy protocol⁵, large-scale confirmatory studies of these treatments have been disappointing⁶⁻¹⁰). As a result, renewed attention has shifted towards identification of sepsis-induced abnormalities at the cellular and microcirculation level, such as dysfunction of mitochondria (the parts of cells which generate energy), endothelium (the lining of blood vessels which plays a role in controlling blood supply to tissues) and cellular oxygen metabolism despite adequate tissue blood supply¹¹.

Therapies aiming to correct oxygen metabolism, mitochondrial, and endothelial dysfunction have been dubbed “metabolic resuscitation”^{12,13}.

2.2 Preliminary Data:

Clinical studies of Vitamin C in critical illness date back 40 years¹³. More recent work in burn victims had demonstrated that Vitamin C supplementation was able to reduce fluid volume resuscitation to achieve hemodynamic (blood pressure) resuscitative goals¹⁴. Subsequent studies have demonstrated trends in decreased multiorgan failure support with broad antioxidant supplementation¹⁵.

Further studies expand on the positive therapeutic potential of Vitamin C supplementation for sepsis. Fowler et al performed a Phase 1 randomized controlled trial of 24 patients admitted to the Intensive care unit with sepsis. Subjects received either low dose or high dose Vitamin C supplementation or placebo. Whilst the primary endpoint of safety and tolerability was met, most intriguing was the finding of a dose dependent improvement in SOFA score (surrogate for organ failure) as well improvement in inflammatory markers¹⁶. These findings were expanded upon by Zabet et al in 2016, who tested the effect of Vitamin C supplementation had upon vasopressor dose and duration of therapy. Twenty four patients admitted to a surgical ICU were randomized to receive placebo or Vitamin C supplementation. Not only did the cohort receiving Vitamin C experience significant reduction in dosing requirement and duration of therapy there was a significant reduction in mortality¹⁷. Most recently a before-and-after retrospective study of a combination of Vitamin C, thiamine and hydrocortisone supplementation in severe sepsis and septic shock patient also demonstrated a remarkable survival benefit in the supplemented patients compared to usual care¹⁸.

Together, these preliminary results suggest that supplementation of Vitamin C may play an important role in the metabolic resuscitation of patients with septic shock. While intriguing, the limitations of the non-blinded before-and-after study combined with a history of false-positive results in adjuvant therapy trials in sepsis (e.g. activated protein C administration^{19,20}, atorvastatin administration²¹) temper these dramatic results, and further validation via prospective analysis is justified and necessary to clarify a possible novel therapeutic approach.

2.3 Existing Literature:

The pathophysiological abnormalities in sepsis and septic shock which are the targets of metabolic resuscitation include diminished vascular tone (improper relaxation of the muscles controlling blood vessel diameter), porous microvascular junctions caused by barrier dysfunction (leakiness of the cell layer surrounding blood vessels), and inappropriate leukocyte adhesion with activation of inflammation microvascular coagulation cascades (dysregulated immune system activation)²². While the pathophysiology of sepsis is multifaceted, metabolic derangements are common, including several antioxidant vitamin levels which invariably fall during sepsis²³. These deficiencies include Vitamin C (Vitamin C), and thiamine with low levels of each correlating with progressive multiorgan failure and death²⁴⁻²⁷. Emerging clinical data (as outlined in section 2.2) as well as laboratory findings suggest that supplementation of Vitamin C during septic shock may play a key role in metabolic resuscitation by resolving microvascular dysfunction^{28,29}, augmenting vascular tone, and providing a cofactor for catecholamine (steroids such as adrenaline) synthesis³⁰.

3.0 Study Endpoints/Events/Outcomes

3.1 Primary Endpoint/Event/Outcome:

First outcome endpoint for Specific Aim 1: all-cause mortality measured at ICU discharge.

Second outcome endpoint for Specific Aim 1: all-cause mortality measured at 28 days post Day 0.

3.2 Secondary Endpoint(s)/Event(s)/Outcome(s):

Outcome endpoint for Specific Aim 2: Difference in clinical outcomes between both groups at ICU discharge. Specific secondary endpoints may include, depending on power and final enrollment:

- a. Duration of vasopressor therapy post administration of Vitamin C (or placebo). Conclusion of vasopressor therapy will be defined as the time point when pressors are stopped, following which they are not restarted for 24 hours.
- b. Duration of ICU stay post administration of Vitamin C (or placebo).
- c. Time to lactate clearance post administration of Vitamin C (or placebo). Time of lactate clearance will be defined as the first time point at which measured lactate level drops below the normal level as defined by the measuring laboratory.
- d. Rate of lactate and procalcitonin clearance over 24, 48 and 96 hours following Vitamin C (or placebo) administration (in patients for whom values are available). Defined as the change in lactate and procalcitonin level from the initial measurement to the measurement at the designated time point if available, or closest measurement within 4 hours of the designated time point.
- e. Duration of mechanical ventilation post administration of Vitamin C (or placebo). Cessation of mechanical ventilation will be defined as the time of extubation following which re-intubation is not required for a full 24 hours.
- f. Incidence of need for renal replacement therapy during the 96 hour drug administration period
- g. Change in serum creatinine at 24, 48, 72, and 96 hours after Vitamin C (or placebo) administration compared to level at enrollment (in patients for whom values are available). The measurement closest in time to the designated time-point (within 12 hours) will be used. Patients who are dialysis-dependent at baseline or are currently receiving renal replacement therapy will be excluded from this endpoint.
- h. Change to SOFA and/or APACHE scores from initiation of Vitamin C (or placebo) as measured at 24, 48, 72, and 96 hours.
- i. Total intravenous fluid administered from presentation until various intervals (3 hours, 6 hours, and 24hours), until resolution of shock, and from Vitamin C (or placebo) administration until resolution of shock.
- j. Effect of standard of care medications including corticosteroids as a sub-group analysis.

Outcome endpoint for Specific Aim 3: In general, clinical and biochemical characteristics associated with Vitamin C responsiveness will be examined. Specifics include:

- a. Assessment of whether time from onset of septic shock to receipt of Vitamin C (or placebo) influences effectiveness of Vitamin C therapy.
- b. Treatment effects as associated with or without initial presentation of inflammatory response

- Fever versus hypothermia
- Leukocytosis versus leukopenia
- Surgical versus medical source control
- c. Biobanking of blood specimens for future assessment of:
 - Vitamin C levels
 - Cytokine and chemokine levels
 - Danger associated molecular patterns (DAMPs)
 - Markers of necroptosis (RIP1 and RIP3)
 - Mitochondrial DNA and RNA for gene expressions
 - Genetic features favorable to Vitamin C therapy

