- d. The infusion will be protected from light with an amber bag. IV tubing will not be protected from light.

2. Preparation of Placebo

- a. The placebo infusion bag will be a 500 mL Normal Saline Infusion bag.
- b. The placebo infusion will be protected from light with a brown bag in the same manner as the active drug. IV tubing will not be protected from light.

3. Drug Administration

- a. The 1000mg bolus (100 ml) of active drug or placebo will be administered over 30 minutes from the active drug or placebo continuous infusion bag, respectively.
- b. After the initial bolus is complete, the continuous infusion will run at a rate of 250mg/hr (25 mL/hour).
- c. A dedicated line for the Ascorbic Acid or placebo infusions is not required. IV compatibility with other IV solutions should be checked per standard of practice.
- d. Infusion can be administered peripherally.
- e. Infusion will be stopped if the participant transitions to comfort care measures only

4.3 IND/IDE:

Not applicable, exempt. There is no intent to report to the FDA for a new indication, nor intent of this study is to support a significant change in the advertisement of Vitamin C. The administration of Vitamin C or placebo in septic shock population does not significantly increase risk or decrease acceptability of risk with its proposed route of administration and dosing.

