8.0 Study Duration

Each participant will be on the study drug for up to four days. There is a final data collection time point at 28 days but no participant interaction is needed for this; it will be chart review only.

It is expected that it will take up to 1.5 years to enroll all study participants. It is expected that it will take up to 2 years to complete all study procedures and data analysis.

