13.0 Withdrawal of Participants

13.1 Withdrawal Circumstances:

Participants can be withdrawn from the infusion or the study completely at any time by the study clinician or their personal clinician for:

1. A serious adverse event suspected to be related to the study drug.
2. Any suspicion that further involvement would jeopardize medical care.
3. Transitioning to comfort care measures only

Unblinding of treatment allocation will occur when such information would be critical to the ongoing care of the participant. Researchers will work with IDS and the research pharmacist on the unblinding procedures.

13.2 Withdrawal Procedures:

At the point of a participant-requested withdrawal, the infusion will be halted and no further direct interaction will occur. Data collection including Day 28 medical record review will still be conducted.

13.3 Termination Procedures:

Data will continue to be used and analyzed after withdrawal or termination.

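### The first of two unranked primary endpoints, mortality at ICU discharge, stops counting deaths at a time the drug is hypothesised to bring forward, so faster ICU exit alone could be reported as a primary survival gain

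*Combined protocol and SAP*

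**What the plan says.** Section 3.1 gives Specific Aim 1 two primary endpoints: "First outcome endpoint for Specific Aim 1: all-cause mortality measured at ICU discharge" and "Second outcome endpoint for Specific Aim 1: all-cause mortality measured at 28 days post Day 0". Neither is placed above the other.

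Section 1.1 lists the Aim 2 outcomes as "duration of vasopressor therapy, duration of ICU stay, lactate clearance, and organ failure" and adds "Hypothesis Aim 2: Compared to placebo, moderate-dose Vitamin C will improve clinical outcomes". For ICU stay, improvement means a shorter stay. Section 3.2 repeats ICU stay as secondary endpoint b.

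Comfort care appears in two operational rules. Section 4.2 says "Infusion will be stopped if the participant transitions to comfort care measures only", and Section 13.1 lists "Transitioning to comfort care measures only" among the reasons for withdrawal. Neither rule says how such a patient is scored for mortality.

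On follow-up, Section 8.0 says "There is a final data collection time point at 28 days". Section 5.3 adds that this review draws on a clinical data repository as well as the chart, so that deaths outside hospital are found.

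Section 16.1 compares mortality between arms by chi-square, with a logistic model, and does not say at which time point. Section 16.2 bases the sample size on hospital mortality, which is neither of the endpoints in 3.1.

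**The concern.** Aim 1 asks whether patients survive. Mortality at ICU discharge mixes that question with how long patients stay in the ICU. Suppose two patients both die on Day 9. One left the ICU on Day 7 and died on the ward, so was alive at ICU discharge. The other was still in the ICU and counts as a death. If treatment shifts patients from the second situation to the first, the endpoint improves although nobody lives longer. The same applies to a patient who leaves the ICU alive under comfort care and dies soon afterwards.

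The protocol hypothesises this kind of shift. Because the two primary endpoints are unranked and the tested time point is not named, a significant ICU-discharge result could be reported as success on the primary aim even if 28-day mortality were equal in the two arms.

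**Working it through.** **The plan's own figure.** Section 16.2 states 62 per arm for 80% power to detect a 20% decrease at two-sided 0.05. It gives no control rate. Using the pooled-variance formula without continuity correction,

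n = [1.96·√(2p̄(1−p̄)) + 0.8416·√(p₁(1−p₁) + p₂(1−p₂))]² / (p₁−p₂)²,

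an assumed 30% v 10% (p̄ = 0.20) gives 61.6, rounded up to 62, with power 0.803. So 62 is reproduced if the 20% means absolute points from a 30% control rate. A relative 20% drop from the 25% to 50% mortality quoted in Section 2.1 would need 1,094 down to 388 per arm, so the absolute reading is the one that fits.

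**Model for the bias.** Let M be 28-day mortality, equal in both arms (no true effect). Let f be the share of those deaths that occur after ICU exit. Take all deaths as falling by Day 28. Then

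ICU-discharge mortality = M × (1 − f)

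false gain = M × (f on Vitamin C − f on placebo).

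**Inputs.** From the plan: 62 per arm, two-sided 0.05 and the chi-square test (Section 16). Assumed: M = 35%, which lies inside the 25% to 50% of Section 2.1, and f = 10% on placebo. The documents give no figure for f in either arm, so the Vitamin C value is varied.

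The last column is an exact binomial enumeration of the uncorrected chi-square test with 62 per arm.

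| f on Vitamin C | ICU-discharge mortality, placebo | ICU-discharge mortality, Vitamin C | False gain (points) | Chance of significance favouring Vitamin C |
|---|---|---|---|---|
| 10% | 0.35 × 0.90 = 31.5% | 0.35 × 0.90 = 31.5% | 0 | 2.5% |
| 15% | 31.5% | 0.35 × 0.85 = 29.75% | 1.75 | 4.0% |
| 20% | 31.5% | 0.35 × 0.80 = 28.0% | 3.5 | 6.2% |
| 30% | 31.5% | 0.35 × 0.70 = 24.5% | 7.0 | 13.7% |

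**Range over M.** With M from 25% to 50%:
- f of 10% v 20% gives a false gain of 2.5 to 5.0 points and a chance of 5.0% to 8.9%.
- f of 10% v 30% gives 5.0 to 10.0 points and a chance of 9.8% to 21.5%.

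**Direction.** The sign follows f. If Vitamin C lengthened ICU stay, f would be lower on Vitamin C and the endpoint would be biased against it.

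**The fixed window.** On 28-day mortality both arms have M, whatever f is. The expected difference is 0 and the one-directional error stays near 2.5%.

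**The case against.** The strongest reply is that the next line of Section 3.1 already deals with this. 28-day mortality is also primary, its window is fixed, and Section 5.3 collects deaths outside hospital. The Day 9 ward death is counted there, as is any patient transferred out under comfort care who dies by Day 28. This stands, and it limits the point: the two results side by side would expose a false gain. It follows that the harm is not independent of which endpoint decides. It arises only because nothing in 3.1 or 16 stops the ICU-discharge result from being claimed alone.

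A reader might infer two stronger things that the documents do not support.

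- **That the plan has a rule scoring comfort-care patients as survivors.** It has no scoring rule. A patient who dies in the ICU under comfort care is counted as a death. Only one who leaves the ICU alive escapes the count, and the documents do not say how often that happens.
- **That a patient still in the ICU at Day 28 can have no value.** Section 3.1 does not cap this endpoint at Day 28, and Section 18.2 allows deaths to be recorded whenever the site learns of them. What can be said is that final data collection falls at Day 28 and no rule covers such a patient.

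It is also fair to say that the larger figures rest on Vitamin C doubling or tripling the share of deaths after ICU exit while preventing none. With equal shares there is no bias, and with 10% v 15% it is small.

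Blinding is a weaker reply. It keeps knowledge of allocation out of discharge decisions, but the bias described here comes from a real effect of the drug on recovery time.

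**Conclusion.** The point holds as a weakness in how the primary aim is defined. The first-listed primary endpoint depends on a time that the protocol hypothesises treatment will change, and the plan does not put the sound endpoint ahead of it. Under the assumptions above, the false gain runs from 0 to 7 points against a 20-point design effect, and the chance of a spurious significant benefit from about 2.5% to 13.7%. Which value applies cannot be settled from the documents, because they give no rate of death after ICU exit. The existence of the bias needs only that this share differ between arms; its direction and size are conditional on that difference. The comfort-care and Day 28 cases are unstated rules, not stated errors.

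**What to change.** - **3.1:** make all-cause mortality at 28 days after Day 0 the single primary endpoint.
- **16.1:** name it as the endpoint compared by the chi-square test and modelled by the logistic regression.
- **16.2:** replace hospital mortality with the same endpoint and state the control rate assumed. If that rate is 30% falling to 10%, 62 per arm is unchanged.
- **3.2:** report ICU-discharge mortality as a secondary, descriptive figure beside 28-day mortality. Show patients discharged from the ICU under comfort care, and those still in the ICU at Day 28, as separate categories.

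A composite that counts death within the index hospital stay would not be a remedy, since it only replaces ICU exit with hospital exit.

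The cost is small. Day 28 vital status is already collected. The one added item is disposition at ICU discharge, taken from charts already under review. The price is that ICU mortality no longer carries a primary claim.

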5.0 Procedures Involved

5.1 Study Design:

This is a multi-site, randomized, double-blind, placebo-controlled trial comparing a regimen of moderate-dose (6000 mg per day) Vitamin C supplementation versus placebo for the treatment of patients presenting to the ICU with septic shock. Both groups will continue to receive all other standard of care measures for septic shock as clinically indicated. Groups will be enrolled and receive study drug/placebo for 4 days (96 hours) or until 24 hours post-last pressor dose, whichever is sooner.

5.2 Study Procedures:

When a potentially eligible participant is identified, the PI or other clinical research team member will approach the individual with floor staff permission and coordination to explain the research.

PROTOCOL TITLE: Evaluating Vitamin C in Septic Shock: A Randomized Double Blind Control
Trial

VERSION DATE: March 17, 2020

After signing the consent and completing eligibility procedures, IDS will be notified. IDS will perform randomization and dispense appropriate study drug/placebo infusion materials.

Infusions must be started within 24 hours post-presentation of septic shock. Those participants who consent but cannot start an infusion within 24 hours will still follow all research procedures related to data collection except for banking of biospecimens.

Participants randomized to Vitamin C will receive IV parenteral Vitamin C; with a 1000 mg bolus to start and followed by a continuous infusion at 250 mg/hr for four days or off pressors for 24 hours, whichever is sooner. Placebo will be given as a matched infusion on the same schedule.

Chart review will take place at 24 hour time periods (Day 0, 1, 2, 3, and 4).

Blood draws for biobanking will occur at Day 0, 1, and 3 (0, 24 and 72 hours), 25 mL on day 0, and then 20 mL on days 1 and 3. Patients discharged from the hospital will not undergo blood draws following discharge. Those still in the hospital, any floor or unit, will have blood drawn if clinically possible. Blood draw will be based on a convenience sample only. Blood draw will only be done when study clinician is available and when time is available for processing and transporting. Not all participants will have all, or any, blood draw done for biobanking.

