9.0 Study Population

9.1 Inclusion Criteria:

- Capability to provide written consent from participant or legally authorized representative (LAR) if the participant is unable or incapacitated due to severity of illness.
- Age \geq 18 years
- Septic shock as pragmatically defined as:
 - Order for intravenous antimicrobials with either procalcitonin $>$ 2 ng/mL within 24 hours of enrollment OR other clinical suspicion of infection or confirmed infection AND
 - Hypotension requiring vasopressor therapy, despite fluid resuscitation of at least 30 mL/kg ideal body weight AND
 - Lactate $>$ 2 mmol/L 24 hr prior to enrollment AND

- Presence of sepsis defined as equal to or greater than 2 SIRS criteria and/or acute increase in qSOFA score of 2 points or more.
 - *SIRS criteria: 1) Temperature greater than 38° or less than 36° Celsius. 2) Heart rate greater than 90 beats per minute. 3) Respiratory rate greater than 20 breaths per minute OR arterial carbon dioxide tension less than 32 mmHg. 4) White blood cell count greater than 12,000 cell/ μ L, less than 4,000 cells/ μ L, OR band cells greater than 10% of the total white blood cell population.*
 - *qSOFA: 1 point each is assigned for: 1) systolic blood pressure below 100, 2) respiratory rate greater than 22, and 3) mental status not at baseline.*

9.2 Exclusion Criteria:

- Unable to start infusion within 24 hours of septic shock identification
- Currently pregnant or breastfeeding
- Patient to receive comfort measures only
- Cardiac Arrest
- Cardiovascular Surgery patients receiving prophylactic peri-operative antibiotics < 48 hours post-operation
- Participation in another study involving an investigational product within 30 days of the baseline visit
- Allergy to Vitamin C
- History of nephrolithiasis
- History of G6PD deficiency
- ESRD patients, transplant eligible on dialysis currently taking vitamin C supplementation
- Clinical course that treating clinician decides would preclude safe participation

9.3 Screening:

Potential participants will be identified by clinic staff at sites identified in Section 23.0. Once identified, the study team will review the medical record for basic eligibility and research opt-out status. Once the medical record has been reviewed, the investigator or coordinator and floor staff will approach the potential participant to explain the study.

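### The starting value for lactate and procalcitonin clearance (Section 3.2, item d) is undefined and may predate infusion by a day or more; item c does not require lactate to be raised when its clock starts

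*Combined protocol and SAP*

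**What the plan says.** Section 3.2 item d concerns the "Rate of lactate and procalcitonin clearance over 24, 48 and 96 hours following Vitamin C (or placebo) administration". It is "Defined as the change in lactate and procalcitonin level from the initial measurement to the measurement at the designated time point", or failing that the "closest measurement within 4 hours of the designated time point". The later value therefore has a 4-hour window. The starting value has neither a window nor a definition.

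Item c measures time to lactate clearance from administration. The event is "the first time point at which measured lactate level drops below the normal level as defined by the measuring laboratory". Nothing is said about participants whose lactate is already normal when the infusion starts.

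Neighbouring items do name an anchor: item g (creatinine) uses the level at enrollment, and item h (SOFA/APACHE) uses initiation of study drug.

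Two timing rules bear on this. Section 9.1 requires a lactate above 2 "mmol/L 24 hr prior to enrollment". Section 5.2 states: "Infusions must be started within 24 hours post-presentation of septic shock". Section 5.3 defines Day 0 as the time of first infusion.

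For Aim 2, Section 16.1 compares continuous outcomes with a two-sample t test. It adds covariate-adjusted regression without naming the covariates.

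**The concern.** In item d the end of the interval is tied to infusion and the start is not. An analyst who takes the words literally would use the first charted lactate, often the one that qualified the patient. The change would then include the response to resuscitation before any study drug was given, over a period that varies by patient. An analyst who reads the item as starting at Day 0 would compute something different. Lactate clearance is named in Specific Aim 2, and two workable readings leave room for the choice to be made after results are seen.

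Item c has a different gap. Eligibility looks back from enrollment, so it does not ensure a raised lactate at infusion. A participant who is already normal has no clearance left to observe, and the recorded time may only reflect when the next sample was drawn.

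**Working it through.** The documents give no effect, SD or power for these endpoints, so there is no planned figure to reproduce. The gap comes from the documents. Everything about its effect below rests on assumed kinetics.

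**1. The possible gap.** Gap = (enrollment − lactate time) + (infusion − enrollment). The first term can reach 24 h (Section 9.1). The second is under 24 h, because infusion must start within 24 h of shock identification (Section 5.2) and enrollment falls in between.
- If enrollment is close to infusion, the gap is 0 to 24 h, and the nominal 24 h change covers 24 to 48 h.
- The theoretical limit is just under 24 + 24 = 48 h.

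**2. How much of the change is pre-treatment.** Assume exponential decline with half-life h, gap g and follow-up T = 24 h:

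share before infusion = (1 − 2^(−g/h)) / (1 − 2^(−(g+T)/h))

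| Gap | h = 12 h | h = 24 h | h = 48 h |
|---|---|---|---|
| 6 h | 36% | 27% | 24% |
| 12 h | 57% | 45% | 39% |
| 24 h | 80% | 67% | 59% |

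Example, g = 24 and h = 12: (1 − 0.25) / (1 − 0.0625) = 0.80.

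**3. Noise or bias.** Write L0 for the initial value, Li for the value at infusion and L24 for the value at 24 h. Then L0 − L24 = (L0 − Li) + (Li − L24). Study drug can act only on the second term. Under blinded randomisation the first has the same expectation in both arms, so it adds variance and leaves the expected difference unchanged. With no treatment effect simulated, type I error for raw change from the initial value was 5.1%.

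**4. Re-anchoring alone.** Assume mean initial lactate of 3, 4 or 6 mmol/L, median half-life 18 h, gap uniform on 0-24 h, and post-infusion decline 25% faster on treatment. With n = 62 per arm, power ≈ Φ(difference/SD × √(n/2) − 1.96).

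| Mean initial lactate | Difference | SD, from initial | SD, from infusion | Power, from initial | Power, from infusion |
|---|---|---|---|---|---|
| 3 | 0.142 | 0.720 | 0.484 | 19% | 37% |
| 4 | 0.189 | 1.242 | 0.764 | 13% | 28% |
| 6 | 0.284 | 2.323 | 1.362 | 10% | 21% |

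First row: 0.142/0.720 × √31 − 1.96 = −0.86, and Φ(−0.86) = 0.19.

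**5. Re-anchoring plus adjustment.** Assume initial lactate with median 4.5 mmol/L and log SD 0.5, decline 2.5%/h (SD 2%/h), start delay uniform on 0-24 h, and lactate 22% lower at 24 h on treatment. Power at 62 per arm:
- raw change from the initial value: 24%
- log model adjusted for the initial value: 44%
- raw change from the last pre-infusion value: 52%
- log model adjusted for the last pre-infusion value: 84%

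Variants, comparing the first and last of these methods: 23% to 86% in a repeat with 0-24 h delay, 37% to 81% with 0-6 h delay, and 23% to 74% when the last value may be up to 6 h old.

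**6. Already normal at infusion (item c).** Taking 2 mmol/L as the limit, a patient is still above it at infusion only if L0 > 2 × 2^(g/h). That is 2.18 for g = 6, h = 48; 2.83 for g = 12, h = 24; and 8.0 for g = 24, h = 12. The simulated share already below 2 mmol/L ran from about 1% to 57% across the assumptions tried.

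**The case against.** The strongest reply is that item d can be read as starting at Day 0. It speaks of clearance over 24, 48 and 96 hours after administration, and the schedule places a baseline chart review at Day 0. On that reading the intervals are as stated. This stands as a possible reading, but the text does not require it, and items g and h show that an anchor could have been named.

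A reader might infer that pre-treatment decline confounds the treatment effect. The documents do not support that: the trial is randomised and double-blind, and step 3 shows a loss of precision only. Nor does the problem extend to item c, whose clock starts at administration; its gap is the missing at-risk condition. Even there, a lactate that drops below normal could be read as having to cross from above, so scoring at the next draw is a possibility, not a stated rule.

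The plan also does not say whether the change is absolute, relative or per hour, so the raw differences simulated here are one interpretation. Section 16.1 already mentions adjusted regression. But its covariates are unnamed and the t test is listed first, so adjustment for the starting value is not assured.

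Finally, the power contrast combines three changes: anchor, log scale and adjustment. Re-anchoring alone gains less, for example 39% to 50% when delays are 0-6 h, or 28% to 43% when pre- and post-infusion decline are independent. That is correct and limits what can be claimed for the anchor itself.

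**Conclusion.** The concern holds as a gap in definition. Item d leaves its baseline open and permits one taken a day or more before infusion. Item c has no condition that the participant be at risk of the event. The consequence is lost precision and a rate that may not match its stated interval.

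The size depends on kinetics that the documents do not give. At 62 per arm and an assumed 22% effect, power was about 23-37% for raw change from the initial value, and about 74-86% for the log model adjusted for the last pre-infusion value. The direction was the same in every setting tried. A reader might take away that about a fifth of participants will already have cleared at infusion; that figure comes from one set of assumptions and cannot be derived from the documents.

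These endpoints are optional under Section 3.2, and the mortality analysis is untouched. This is a minor improvement, worth making because it is cheap.

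**What to change.** Before unblinding, amend Sections 3.2 and 16.1 as follows.

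- **Item d, baseline:** the last lactate or procalcitonin value at or before infusion start, within a stated window. State which anchor applies to participants who never start the infusion, since Section 5.2 keeps them in data collection.
- **Item d, analysis:** make the main comparison a regression of the follow-up value at each time on treatment and that baseline, in place of the unadjusted t test on change. The log scale is sensible for skewed values.
- **Item c:** restrict to participants above the laboratory normal at that same baseline, and report how many are excluded in each arm.

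The cost is wording, with no added visits or blood draws. Participants without a recent pre-infusion value leave item d, and those without one or already normal leave item c. Losses may be greater for procalcitonin, because Section 9.1 does not require it of everyone at entry.
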